8.2.1. Inclusion Criteria

Patients must meet all of the following inclusion criteria to be eligible for inclusion in the study:

- Adult patients (males and females) 18 years of age and over.
- Patients being treated with SU as 1st line treatment according to the approved therapeutic indication.
- Histologically confirmed diagnosis of adv/mRCC (clear cell RCC as well as non-clear cell RCC) with measurable disease according to RECIST 1.1.
- Evidence of a personally signed and dated informed consent document indicating that the patient (or a legally acceptable representative) has been informed of all pertinent aspects of the study.

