8. RESEARCH METHODS

8.1. Study Design

OPTIMISE is an international (AfME), prospective, non-interventional, non-controlled, observational multicenter study.

Patients will be enrolled from several AfME countries including Algeria, Morocco, Tunisia, Egypt, UAE, Qatar & South Africa. Investigators will be specialists, in charge of adv/mRCC. These sites involved (at least when performing feasibility) will be representative of their respective country in terms of practice. Participating physicians will not be influenced in their decision making and routine proceedings in any way.

[figure not shown]
Primary outcome measure will assess PFS in patients receiving the SU and in patients receiving a second line treatment post SU; as well as TTF for patients with adv /mRCC.

Patients will be enrolled when they start a treatment with SU on 1st line. Patients enrolled at SU initiation, will be followed-up whatever the post SU-2nd line treatment is (AXI, other drugs, no further active treatment, (supportive care)). The possible 1st and 2nd line sequences of treatment under investigation (ie, patient pools) will be ([Figure 1](#)):

- SU-AXI.
- SU- other second line treatment (sorafenib, pazopanib, everolimus, temsirolimus, other).
- SU- not further active treatment (supportive care). The study will include a prospective data collection:
 - Prospective data will also be collected for all patients enrolled in the study at SU- 1st line level, irrespective of 2nd line treatment, or no further active treatment;
 - Prospective data in terms of medical treatment records, will be collected for all 2nd line patients.

The inclusion period of eligible patients is planned for 12 months, with minimum of 1 year follow-up period. Patients will be followed-up from their enrollment to the end of the study follow-up period.

Figure 1. Study Flow Chart

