8.2. Setting

The study will enroll patients according to the eligibility criteria in participating countries across Africa Middle East. The recruiting centers will be representative of each country involved in terms of care management systems, of size and of practices (at least when performing feasibility).

Any patient who meets the eligibility criteria will be invited to participate in the study with no biased selection by the investigators. The enrollment visit will be performed at the time of the patients' inclusion, after the patients' acceptance of enrollment in the study.

Data will come from medical records and will be collected in routine clinical practice. The enrollment visit will comprise a first section on patients' eligibility for every patient whatever pool they belong to and a second section on SU treatment started at the inclusion.

Follow-up will be ensured during visits in the context of usual patients' care management (non-interventional study). No extra visits will be required by the protocol of the study.

As long as the patients are treated with SU as first line, every visit to the center will be recorded. In accordance with ESMO guidelines and physicians clinical practice is real life, follow-up visits are approximately expected:

- During SU treatment: every 6 weeks (every cycle) with tumor assessment approximately every 3 months with respect to the clinical practice.
- When patients come off SU treatment (and after receiving the SU-2nd line sequence) they will be followed-up every 6 months (separate form) for survival until the end of the study.
- A deviation of +/- 6 weeks (1.5 months) is acceptable window for the follow-up visits.

As the inclusion criteria (patients being treated with SU in 1st line according to the approved therapeutic indication), the medication prescribed within the regular practice of the physician. In addition, as of the non-interventional nature of the study, there will be no specific requirements with regards to the treatment process. The physician will determine dosage and duration of the treatment, guided by the local country approved Prescribing Information and according to his assessment of the individual therapeutic needs of the patient.

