8.5.1. Screening/Baseline

The following observational parameters are recommended to be collected at the screening/baseline Visit (Visit 1: Day 0):

- Informed Consent.
- Inclusion and exclusion criteria check.
- Patient Demography (date of birth, gender, race, country/nationality).
- Sites of Metastasis.
- Medical History (including previous history of myocardial infarction (including severe/unstable angina), coronary/peripheral artery bypass graft, symptomatic CHF, cerebrovascular accident or transient ischemic attack, pulmonary embolism, hypothyroidism, hypertension and diabetes mellitus).
- Physical examination (General, Lungs, Heart, Musculoskeletal, Genitourinary, Neurological, Lymph nodes, Skin, Abdomen and Other).
- Tumor stage and prior treatment history (including the dose and schedule of SU being 1st line, duration of various therapies).
- Baseline Lab Tests (as per institutional routine practice):
 - Hematology: hemoglobin (Hgb), platelet count (Plt), white blood count, WBC White blood cell differentials (%) -Neutrophils, Lymphocytes, monocytes, basophils and eosinophils;
 - Chemistry: total bilirubin, alanine aminotransferase (ALT), aspartate aminotransferase (AST), alkaline phosphatase, lactic dehydrogenase (LDH), albumin, sodium, potassium, Magnesium, chloride, calcium, blood urea nitrogen (BUN), phosphorus, creatinine and uric acid;
 - Thyroid function tests (serum): T3, T4, and TSH;
 - Urinalysis: Urine Protein.

- Concomitant medications (a window period of 28 days prior to the start of the study treatment, during the study and up to 28 days post the last dose of treatment applies).
- Adverse Events Assessment.
- Performance Status (ECOG).
- Vital Signs; including body weight (BMI) and blood pressure.
- QOL questionnaire (FKSI 19) ([Appendix 1](#)).

N.B. please refer to [Section 8.4.1](#) for the recommended schedule interval (a deviation of +/- 6 weeks (1.5 months) is acceptable window for the visits.

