2.2. Study Design

▪ Global design

- OPTIMISE is an international prospective, non-interventional, non-controlled, observational multicenter study.
- Patients would be enrolled from several AfME countries including Algeria, Morocco, Tunisia, Egypt, UAE, Qatar and South Africa.
- Investigators will be specialists in charge of adv/mRCC where sites involved will be representative of their respective countries in terms of practice
- Participating physicians will not be influenced in their decision making and routine practice in any way.

▪ Populations

- Patients will be enrolled when newly diagnosed and when the treatment with SU is chosen as 1st line
- Patients enrolled at SU initiation, will be followed-up whatever the post 2nd line SU- different sequence treatment is (AXI, other drugs, no further active treatment OR supportive care).
- The possible 1st and 2nd line sequences of treatment under investigation (i.e. patient pools) will be as follows:
 - SU-AXI
 - SU- other second line treatment (sorafenib, pazopanib, everolimus, temsirolimus, other)
 - SU- not further active treatment (supportive care)
- The population of interest has the below inclusion and exclusion criteria ;
Inclusion criteria:
 - Adult patients (males and females) 18 years of age and over.
 - Patients being treated with SU as 1st line treatment according to the approved therapeutic indication.
 - Histologically confirmed diagnosis of adv/mRCC (clear cell RCC as well as non-clear cell RCC) with measurable disease according to RECIST 1.1
 - Evidence of a personally signed and dated informed consent document
Exclusion criteria:
 - Patients being treated with cytokines or any other treatment other than SU
 - Patients presenting with a known hypersensitivity to SU or its metabolites will not be included in the study per the label.

▪ Data sources

- Data will be collected in routine clinical practice and from medical records
- A case report form (eCRF) will be used for data collection which should be signed by the investigator.
- An investigator performs an assessment of new or ongoing adverse events, relative to a patient's baseline history, at each study visit.
- Generally, the identification of new or ongoing adverse events is determined till the last scheduled visit. CTCAE version 4.0 will be used for the grading of AEs in the eCRF.

Observation period

- The inclusion period of eligible patients is planned for 12 months, with minimum of 1 year follow-up period.

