5.5. Covariates

- In case of multivariate analyses, baseline characteristics will possibly be used as covariates.
- The final covariates will be selected according to the selection strategy of variables defined in the part 7.6.
- Possible, but not exclusive, baseline covariates related to SU initiation will be limited because of a retrospective part of the data collection, with:
 - Age and sex;
 - ECOG (0, 1, 2, 3, 4), Karnofsky performance status
 - MSKCC risk factors (Favorable, Intermediate, Poor)

- Medical history of hypertension (Yes, No)
- Delay from diagnosis (< 1 year from diagnosis to first metastasis detection/ \geq 1 year)
- Nephrectomy (Yes, No)
- Number of metastatic sites
- The covariates identified previously will be also explored and act as baseline for second line treatment initiation. In this case, other covariates will be:
 - The response to SU treatment in 1st line;
 - Duration of SU treatment, PFS;
 - Previous treatments for primary tumor (surgery, radiotherapy, other);
 - Additional anti-tumor treatments;

6. Handling missing values

- The majority of data will be collected with a website (except for FKSI-19 questionnaires).
- In this website, the input of certain data will be obligatory, limiting the number of missing values, particularly for endpoints.
- Regarding the descriptive analyses of each variable, it will be based on the available data (“observed-case analysis”), considering missing data as non-informative.
- The number of missing data will be documented for each analysis.
- The analysis of the primary endpoint is a survival analysis which is known to efficiently handle missing data: All patients are included in the analysis and missing data are called right-censored data.
- In case of absence of 20% data and over, for a main parameter such as ORR rate, the Hot-deck imputation method could be used. With this method, the missing value is replaced by the observed value of a patient with similar characteristics $X_1, X_2 \dots X_k$. If it does not exist such similar patient, the missing value will be amputated
- A sensitivity analysis will be conducted by the imputation of extreme values. In the one hand, analysis in the most unfavorable situation (i.e. missing data considered as failure) and in the other hand, analysis in the most favorable situation, i.e. missing data considered as success (e.g. for ORR, success is to be responder).

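### The eligibility criterion does not enforce enrolment at SU start, and PFS and TTF run from first dose without delayed entry, so any late entrant would bias both medians upward

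*Protocol*

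**What the plan says.** **Text that places enrolment at SU start**
- Protocol 8.1 (and 3.4): "Patients will be enrolled when they start a treatment with SU on 1st line".
- Protocol 8.2: the enrolment form contains "a second section on SU treatment started at the inclusion".
- SAP 2.2: "Patients will be enrolled when newly diagnosed and when the treatment with SU is chosen as" first-line treatment.
- SAP 8.3 treats the baseline quality-of-life questionnaire as completed at SU initiation.

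**Text that does not enforce it**
- Protocol 8.2.1 requires "Patients being treated with SU as 1st line treatment according to the approved therapeutic indication". Neither 8.2.1 nor the exclusions in 8.2.2 limit the time already spent on SU.
- Protocol 8.2 makes this list the working rule: "Any patient who meets the eligibility criteria will be invited to participate in the study with no biased selection by the investigators".
- SAP 5.5 says that baseline covariates related to SU initiation "will be limited because of a retrospective part of the data collection" and does not explain the phrase. Protocol 3.4 and 8.1 describe prospective collection only.

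**Endpoints and analysis**
- Protocol 3.3.3 and SAP Appendix 3 start PFS and TTF at the first SU dose.
- Protocol 8.9 and SAP 7.4 plan Kaplan-Meier curves and Cox models. Neither mentions delayed entry.
- No section defines an allowed gap between first dose and enrolment.

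**The concern.** A patient who is three months into SU meets every listed criterion. To be enrolled, that patient must have survived three months and still be on the drug. Patients who died or stopped SU in those months could not be enrolled at the same point. An ordinary Kaplan-Meier estimate from first dose nevertheless counts the three months as time at risk.

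The consequence differs between the two primary endpoints:
- **TTF:** the gap is certain to be free of the event, because the patient is still on SU.
- **PFS:** only survival through the gap is certain. Early progressors who stopped SU are also missed, but a patient who progressed and stayed on SU could still enter.

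The expected direction is upward for both, and more strictly so for TTF. The early months matter here: Protocol 6.1.1 cites a chart review in which adverse events led to treatment changes in the first months. The combined PFS, combined TTF and OS share the same time origin.

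**Working it through.** **1. The plan's own figure.** The only calculated design figure is N = 140 for the ORR (Protocol 8.7). The half-width is 1.96 × √(0.37 × 0.63 / 140) = 7.998 points, and the N needed for ±8 points is 1.96² × 0.37 × 0.63 / 0.08² = 139.9. It reproduces, and this point does not affect it. The documents give no planning figure for PFS, TTF or time on SU before enrolment, so the size below is an illustration.

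**2. Inputs**
- True median *m*: 5.9 or 10.5 months. These are the median durations of first-line sunitinib in the community and academic chart reviews cited in Protocol 6.1.1. They are treatment durations, so they are closer to TTF than to PFS.
- Share of enrolled patients already on SU, *f*: 10%, 25% or 50% (assumption).
- Months on SU before enrolment, *a*: 1.5, 3 or 6 (assumption).
- Event times: exponential, with rate λ = ln 2 / *m* (assumption).

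**3. Formula.** For *t* > *a*, the uncorrected curve is S(t) = (1 − f)·exp(−λt) + f·exp(−λ(t − a)). Setting S(t) = 0.5 gives

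median = m × [1 + log₂(1 − f + f × 2^(a/m))].

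**4. Worked case** (m = 10.5, f = 25%, a = 3): 2^(3/10.5) = 1.219; 0.75 + 0.25 × 1.219 = 1.0548; log₂(1.0548) = 0.0769; median = 10.5 × 1.0769 = 11.31 months.

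**5. Uncorrected medians, in months**

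| True median | Share already on SU | a = 1.5 | a = 3 | a = 6 |
|---|---|---|---|---|
| 5.9 | 10% | 6.06 | 6.25 | 6.73 |
| 5.9 | 25% | 6.30 | 6.75 | 7.84 |
| 5.9 | 50% | 6.68 | 7.53 | 9.42 |
| 10.5 | 10% | 10.66 | 10.83 | 11.22 |
| 10.5 | 25% | 10.89 | 11.31 | 12.24 |
| 10.5 | 50% | 11.27 | 12.07 | 13.80 |

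The smallest shift is 6.06 − 5.9 = 0.16 month and the largest is 9.42 − 5.9 = 3.52 months. With f = 0 the shift is zero.

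**6. Does delayed entry repair it?** In a simulation of 200,000 patients with 25% already on SU and prior time uniform over 0 to 6 months, the uncorrected medians were 6.80 and 11.37 months. With late entrants joining the risk set at enrolment they were 5.89 and 10.54, against true values of 5.9 and 10.5.

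The six-month follow-up condition for the efficacy population in SAP 4.1 is a separate matter and is not in these figures.

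**The case against.** The strongest reply is that the documents, read together, describe a cohort of new initiators. Protocol 3.4, 8.1 and 8.2 and SAP 2.2 and 8.3 all say so. The phrase in 8.2.1 can be read as naming the first-line drug rather than the time spent on it, and the exclusion of patients on cytokines in 8.2.2 uses the same form. This stands as a statement of intent. A reader might infer that the study plans to enrol patients already on treatment; the documents do not support that, and nothing in them shows that any would be enrolled.

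The two supporting phrases are also weaker than they look:
- Protocol 8.5.1 lists "prior treatment history (including the dose and schedule of SU being 1st line, duration of various therapies" among the baseline items. This fits recording the starting regimen, which SAP table 9.2 needs, and does not show earlier exposure.
- The retrospective part in SAP 5.5 could mean that diagnosis date, nephrectomy or medical history comes from existing records. It conflicts with the prospective design text, but it does not prove enrolment after first dose.

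A reader might also infer that the gap is guaranteed progression-free. It is not, because no criterion excludes a patient who progressed and stayed on SU. In addition, tumour assessment is expected only about every three months (Protocol 8.2), so little progression would be recorded before month 3 in anyone. The constant-hazard illustration therefore probably overstates the PFS effect for short gaps.

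What the reply does not answer is that intent stated elsewhere does not restrict a list under which every qualifying patient is to be invited, and that the analysis has no safeguard if first dose and enrolment differ.

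**Conclusion.** The point holds as a gap between the stated design and the rule meant to carry it out. The eligibility list admits a patient at any time on SU, and the planned estimator would overstate time on treatment for each such patient. The effect is strict for TTF and looser, but in the same expected direction, for PFS.

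Under the assumptions above the shift in the median is about 0.2 to 3.5 months. That range rests on assumed shares and gaps, exponential times, and medians that are treatment durations. It shows what could happen and is not an estimate of what will. If all patients are enrolled at initiation there is no bias. The wording gap itself is certain; only its numerical consequence is unknown.

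**What to change.** 1. **Eligibility.** Reconcile Protocol 8.2.1 with 8.1 and SAP 2.2, so that SU must be initiated at enrolment or within a short stated window. A window suits a non-interventional study better than insisting that consent always comes before the first dose.
2. **Analysis.** In SAP 7.4, state that a patient whose first dose precedes enrolment enters the Kaplan-Meier and Cox risk sets at the enrolment date. State also that a progression recorded before enrolment cannot count as an event in that PFS analysis. Delayed entry assumes that the timing of enrolment is unrelated to prognosis. At minimum, report PFS and TTF without late entrants as a sensitivity analysis. Apply the same rule to the other endpoints timed from first dose.
3. **Reporting.** Give the number of late entrants and the distribution of the gap.
4. **SAP 5.5.** Explain the retrospective part or reconcile it with the prospective design. Simply deleting the phrase could hide a real feature of the data.

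**Cost.** A few lines of text and slightly more analysis work. PFS and TTF already need the first-dose date, and the consent form is dated, so no new data are required. If late entrants exist, the early part of the curve is slightly less precise. If there are none, the results are unchanged. N = 140 is unaffected.

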8.2.2. Exclusion Criteria

Patients meeting any of the following criteria will not be included in the study:

- Patients being treated with cytokines or any other treatment other than SU in 1st line setting.
- Patients presenting with a known hypersensitivity to SU or its metabolites will not be included in the study per the label.

8.3. Variables

Detailed definitions of variables that will be collected or derived for statistical analyses and summaries will be included in the Statistical Analysis Plan (SAP).

8.4. Data Collection Intervals & Recommended Data Collection Schedule

8.4.1. Recommended Data Collection Schedule

Variables	Screening/Baseline Visit 1 (Day0)	Treatment phase Visit 2-5 (3, 6, 9, 12 month)	Follow-up phase Visit 6-7 (18, 24 month)	EOS
Inclusion/Exclusion Criteria Check	X			
Informed Consent	X			
Patient Demographics	X			
Medical History & Physical examination	X			
Tumor, Site of Metastasis & Prior treatment history	X			
Baseline Lab Tests	X			
Concomitant medications	X	X	X	X
Adverse Event assessment	X	X	X	X
Update in Disease Status	X	X	X	X
Update in Treatment Status/ Change in therapy		X	X	X
Reporting of routine labs collected	X	X	X	X
Performance Status, weight (BMI) & blood pressure	X	X	X	X
QOL Questionnaire (FKSI 19 only)	X	X	X	X

8.5. Study Procedures

Since this is primarily an observational study, there are no patient visits specified by virtue of this protocol. Data to be collected on the electronic case report forms (eCRF) is normally available in patient records.

All data would be collected per the investigator's practice. At any visit, if any of the parameters are not collected, the relevant section in the eCRF will be left blank.

8.5.1. Screening/Baseline

The following observational parameters are recommended to be collected at the screening/baseline Visit (Visit 1: Day 0):

- Informed Consent.
- Inclusion and exclusion criteria check.
- Patient Demography (date of birth, gender, race, country/nationality).
- Sites of Metastasis.
- Medical History (including previous history of myocardial infarction (including severe/unstable angina), coronary/peripheral artery bypass graft, symptomatic CHF, cerebrovascular accident or transient ischemic attack, pulmonary embolism, hypothyroidism, hypertension and diabetes mellitus).
- Physical examination (General, Lungs, Heart, Musculoskeletal, Genitourinary, Neurological, Lymph nodes, Skin, Abdomen and Other).
- Tumor stage and prior treatment history (including the dose and schedule of SU being 1st line, duration of various therapies).
- Baseline Lab Tests (as per institutional routine practice):
 - Hematology: hemoglobin (Hgb), platelet count (Plt), white blood count, WBC White blood cell differentials (%) -Neutrophils, Lymphocytes, monocytes, basophils and eosinophils;
 - Chemistry: total bilirubin, alanine aminotransferase (ALT), aspartate aminotransferase (AST), alkaline phosphatase, lactic dehydrogenase (LDH), albumin, sodium, potassium, Magnesium, chloride, calcium, blood urea nitrogen (BUN), phosphorus, creatinine and uric acid;
 - Thyroid function tests (serum): T3, T4, and TSH;
 - Urinalysis: Urine Protein.

- Concomitant medications (a window period of 28 days prior to the start of the study treatment, during the study and up to 28 days post the last dose of treatment applies).
- Adverse Events Assessment.
- Performance Status (ECOG).
- Vital Signs; including body weight (BMI) and blood pressure.
- QOL questionnaire (FKSI 19) ([Appendix 1](#)).

N.B. please refer to [Section 8.4.1](#) for the recommended schedule interval (a deviation of +/- 6 weeks (1.5 months) is acceptable window for the visits.

8.5.2. Treatment Phase

The following observational parameters are recommended be collected at the Treatment phase, which is visit 2-5 at month 3, 6, 9 and 12.

- Concomitant medications (a window period of 28 days prior to the start of the study treatment, during the study and up to 28 days post the last dose of treatment applies).
- Adverse Events Assessment.
- Update in Disease Status (including PFS, RR, TTR, TTF, OS).
- Update in Treatment Status/ Change in therapy.
- Reporting of routine labs collected.
- Performance Status (ECOG), weight (BMI) and blood pressure.
- QOL questionnaire (FKSI 19) ([Appendix 1](#)).

